11 STATISTICAL CONSIDERATIONS

11.1 STUDY HYPOTHESES

We will compare two interventions to improve the cardiovascular/hemodynamic stability of hemodialysis care by pursuing the following specific aims:

- **Aim 1** Conduct a cluster-randomized controlled trial (CRCT) to test and compare the effects of the above HD facility-level interventions on the primary outcome of dialysis session stability over an intervention period of 24 weeks and a post-intervention follow-up period of 12 weeks.
- **Aim 2** Test and compare the effects of the two HD facility-level interventions on secondary patient-centered clinical outcomes, including: patient symptoms, fluid adherence, dialysis adherence, quality of life, hospitalizations and mortality over the same timeframe.
- **Aim 3** Identify factors associated with successful implementation of the interventions, and ways in which implementation may influence intervention effectiveness.

Our main study hypothesis is that hemodialysis session stability will significantly improve with either multimodal provider education or patient activation interventions, and that multimodal provider education will show a larger improvement. This hypothesis is based on our expectation that some hemodialysis patients might refuse or be unable to participate in peer mentoring, potentially leading to greater penetration of the provider intervention. We will test this main hypothesis and explore this potential explanation of any differential improvement as part of our planned sensitivity, mediation and moderation analyses.

11.2 SAMPLE SIZE CONSIDERATIONS

I. Primary Outcome

For Aim 1, the outcome is a dichotomous measure of HD stability, where an unstable session is defined as the dialysis session stability, where an unstable session is defined as SBP falling below 100 when the starting SBP was ≥ 100 . This outcome will be collected through digital records for all HD sessions of all patients at each facility during the study period. The analysis will be done in two ways. First, as a continuous variable, as described in the power analysis. Using individuals with a minimum of 60 dialysis sessions, the proportion of unstable sessions will be computed. Linear mixed models will be employed to compare individuals in facilities in the two treatment arms to individuals in the non-intervention facilities. Random effects for facility clustering will be accounted for using the MIXED procedure in SAS. As a sensitivity analysis, dialysis session stability will also be examined as a yes/no variable and analysis will be carried out on the longitudinal dataset using logistic regression with a random effect for both patients and facilities, using the GLIMMIX procedure in SAS. The random effects will model the correlations among the measurements at each level. This analysis will use data from all patients, not just those with at least 60 dialysis sessions.

Dialysis facilities will be randomized in a 2x2 factorial design to two study intervention or control groups. Sample size is based on separate tests for each of the two treatment comparisons, and assumes no interaction between treatment types. The primary outcome measure is session instability, particularly IDH, which occurs in approximately 20% of hemodialysis sessions in the usual practice setting in the US. The study is powered to detect a decrease from 20% to 15-

16% in the intervention group. It is assumed that a minimum of 60 hemodialysis patients will be observed for at least 60 dialysis sessions and the outcome will be the proportion of unstable sessions, which we treat as a continuous variable. These proportions among patients in a facility are assumed to be normally distributed with mean 0.20 in the control group and mean between 0.16 and 0.17 in the intervention group (a difference, d , of 0.034 to 0.043), with standard deviation (SD, or 'sigma') assumed to be in the range 0.08 to 0.10. We conservatively assume $n=60$ patients per facility, i.e., a total of $60 \times 20 = 1,200$ patients. The power calculation is robust to changes in number of patients (m), as the calculation of K (number of clusters) only increases by ~ 1 if m is increased to 90. The intraclass correlation coefficient for hemodialysis facilities is assumed to be 0.10. A significance level of 0.05 was assumed in all calculations. Table 5 gives the statistical power to detect a given difference (D , 0.034-0.043), with sigma values of 0.08 and 0.10, and number of clusters (dialysis units, k) per treatment group of 10 (20 facilities total).

Table 5 shows that detecting a difference of ~ 0.03 (i.e., 20% versus 17% of sessions unstable) with 80% power is only feasible with a SD (sigma) of 0.08 or less. If the standard deviation is as large as 0.10, we can detect a difference of 0.043 (i.e., 20% vs. 16%) with 81% power. Put another way, if the smallest variance estimate is correct ($\sigma=0.08$), we have 91% power to detect a 4% difference, and 80% power to detect a 3% difference.

Table 5 - The power is shown to detect a difference in IDH rates (D) between groups assuming 3 possible standard deviations (sigma). The minimum number of facilities (K) is also shown, illustrating some flexibility to accommodate drop-out. Bolded cells show power $\geq 80\%$.						
D	0.034	0.034		0.040	0.043	
Sigma	0.08	0.10		0.08	0.10	
K	10	10		10	10	
Power	80%	61%		91%	81%	

II. Secondary Outcomes

Aim 2 incorporates six outcome measures: (1) patient symptoms (including a patient burden measure, dialysis recovery time, and proportion of sessions with each symptom), (2), fluid adherence (inter-dialytic weight gain), (3) dialysis adherence, (4) quality of life, (5) hospitalization (all-cause and by specific cause), and (6) mortality (all-cause and by specific cause), with will be analyzed at the individual level and summarized at the facility level. Each will use a model format appropriate to the outcome type, but will otherwise follow the model strategy, including the secondary analyses, described for Aim 2 above. The fluid adherence (Interdialytic weight gain), symptom and quality of life analyses, based on continuous outcome measures, will be carried out using mixed models (the MIXED procedure of SAS). Note that the quality of life analyses will be based on data from two time points, one before intervention (the latest KDQOL survey that is within 12 months prior to the start of the intervention) and one during or after intervention (the earliest KDQOL survey that is within 12 months after the start of the intervention), rather than session-specific data as analyzed for the other outcomes. Analyses of missed or shortened HD sessions will employ logistic regression for longitudinal data, as in Aim 1. Analyses of hospitalization and mortality will use logistic regression for individual level data. As part of these models, we will test IDH-related variables (e.g., recent

IDH, frequency of IDH in the past month) as potential predictors. In each case, the appropriate regression diagnostics will be used to assess model fit.

Although the study was not powered specifically for these outcomes, many of the secondary outcomes are continuous variables for which power can be calculated based on effect sizes (multiples of the standard deviation) for any specific outcome, given the sample size of 20 facilities required for Aim 1 analyses. In the power analyses below, we present calculations based on four outcomes, percentage point change in facility proportion of individuals within optimum weight gain ranges between dialysis sessions (interdialytic weight gain between 2-5% of body weight, a measure of fluid adherence), patient recovery time, patient symptoms, and health-related quality of life scores.

(a) Interdialytic Weight Gain (IDWG)

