This design is a *superior choice* in our circumstance to a simple two-arm trial design (i.e., provider education vs. patient activation intervention only) because it provides a control group for testing each intervention. An aim of the project is to translate effective interventions from other settings into the setting of outpatient hemodialysis care. Therefore, there is an inherent need to validate the effectiveness of both interventions in this new environment and patient population (see treatment comparison questions i and ii below), while also comparing their relative magnitudes of effect (see treatment comparison question iii below) and their potentially synergistic or antagonistic effects (see treatment comparison question iv below). If we were to conduct a simple two-arm trial (provider education vs. patient activation only), we would only be able to answer treatment comparison question iii below.

Table 1 - 2 by 2 Factorial Design with Facility and Patient Sample Sizes - # Facilities (# Patients)			
	Patient Activation Intervention		Total
Provider Education	Yes (N_2)	No	
Yes (N_1)	A - 5 (300)	B - 5 (300)	10 (600)
No	C - 5 (300)	D - 5 (300)	10 (600)
Total	10 (600)	10 (600)	20 (1,200)

Therefore, we have designed a trial to answer the following **four treatment comparison questions (see Table 1):**

- i. Provider education vs. no provider education (assumes no interaction between interventions)
 - a. Cells ((A+B) vs. (C+D)) – F test comparison
- ii. Peer mentoring vs. no peer mentoring (assumes no interaction between interventions)
 - a. Cells ((A+C) vs. (B+D)) – F test comparison

Note that all data are re-used in the comparisons for i and ii. This shows a key advantage of the 2x2 design: it allows testing two interventions for the “price of one”. Furthermore, if an interaction is seen (question iv below), then the effect of one intervention can be estimated at each level of the other intervention.

- iii. Comparative effectiveness of provider education alone vs. peer mentoring alone
 - a. Cell B vs. C – F test comparison. The head-to-head comparison of the magnitude of effect for the two interventions is **actually comparing only the interventions alone, in the absence of the other ones.**

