Table 8 above shows the statistical power for a range of ICC, and Control vs. Intervention differences. Power is around 90% or higher to detect differences of 5 or higher for ICC=0.1, and over 80% to detect differences of 6 or higher for ICC=0.2. A difference of 5 would be an effect size of 0.5 (half of the SD), which is considered moderate, and clinically meaningful. In summary, while we do not have data to provide more precise power estimates, the patient symptom burden outcome measure appears to be well powered to detect meaningful effects.

(d) Health-Related Quality of Life (HRQoL). The Kidney Disease Quality of Life instrument (KDQOL) is defined to have a mean of 50 and a standard deviation of 10. A 5-unit change is considered to be clinically meaningful.¹⁶² Based on data to which our team has access from the Dialysis Outcomes and Practice Patterns Study (DOPPS), we determined appropriate facility-level intra-class correlation coefficient (ICC) for HRQoL scores to be 0.07. As shown in Figure 1, we explored power for detectable differences between 1-5 points and a range of sigma between 10 and 12. We determined that with our planned 20 facilities containing 60 patients each, that we are adequately powered (>0.80) to detect differences as small as 4.5 points for all three assumed sigma values. This provides excellent power for detecting a difference between study arms in HRQoL.

Figure 1 - Detectable differences in Health-Related Quality of Life (HRQoL)

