11.4 FINAL ANALYSIS PLAN

Aim 1. Test and conduct a cluster-randomized controlled trial (CRCT) to compare the effects of the above HD facility-level interventions on the primary outcome of dialysis

session stability over an intervention period of 24 weeks and a post-intervention follow-up period of 12 weeks.

Preliminary data analysis. We will compare the four randomized groups to assess covariate balance on participant characteristics, such as demographics. This analysis will test for potential selection bias that might lead to confounding of study results. If study arms are found to be imbalanced on baseline characteristics, in addition to those specified in the analyses below, these characteristics will be included in the regression models as a sensitivity analysis.

Analysis of Primary Outcome. For Aim 1, the outcome is a dichotomous measure of HD stability, where an unstable session is defined as the dialysis session stability, where an unstable session is defined as SBP falling below 100 when the starting SBP was ≥ 100 . This outcome will be collected through digital records for all HD sessions of all patients at each facility during the study period. The analysis will be done in two ways. First, as a continuous variable, as described in the power analysis. Using individuals with a minimum of 60 dialysis sessions, the proportion of unstable sessions will be computed. Linear mixed models will be employed to compare individuals in facilities in the two treatment arms to individuals in the non-intervention facilities. Random effects for facility clustering will be accounted for using the MIXED procedure in SAS. As a sensitivity analysis, dialysis session stability will also be examined as a yes/no variable and analysis will be carried out on the longitudinal dataset using logistic regression with a random effect for both patients and facilities, using the GLIMMIX procedure in SAS. The random effects will model the correlations among the measurements at each level. This analysis will use data from all patients, not just those with at least 60 dialysis sessions.

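### Section 11.2 claims 80% power for a 3-point difference in IDH (20% versus 17%), but the plan's own inputs give about 70%; Table 5 also makes no small-sample allowance for 20 facilities

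*Combined protocol and SAP*

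**What the plan says.** Section 11.2 (I. Primary Outcome) sets the size of the trial. It opens with a target: "The study is powered to detect a decrease from 20% to" 15-16%. It then assumes a control mean of 0.20 and a "mean between 0.16 and 0.17 in the intervention group", with the difference given in brackets as 0.034 to 0.043. Table 5 evaluates differences of 0.034, 0.040 and 0.043 with 10 facilities per group and reports 80%, 61%, 91% and 81%.

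The text around Table 5 says that 80% power for a difference of about 0.03, glossed as 20% versus 17%, is feasible only if the SD is 0.08 or less. For SD 0.10 it says "we can detect a difference of 0.043 (i.e., 20% vs. 16%) with 81% power". It then sums up the SD 0.08 case as "91% power to detect a 4% difference, and 80% power to detect a 3% difference".

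On the test itself, Section 4.1 (II. Factorial Design) labels each factorial contrast "F test comparison". Section 11.4 (Analysis of Primary Outcome) says "Random effects for facility clustering will be accounted for using the MIXED procedure in SAS". Neither section names a denominator degrees-of-freedom method, and Section 11.2 names no formula or reference distribution.

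**The concern.** The plain-language summary attaches 80% to a difference smaller than any that Table 5 evaluates. The 91% beside it belongs to exactly 0.040, so a reader will take the 3% equally literally, and the 20% versus 17% gloss encourages this. Near 80%, power changes quickly with the difference, so dropping 0.4 of a point is not a harmless rounding. Anyone who quotes the sentence would overstate the trial's ability to detect a 3-point fall in the primary outcome.

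There is a second, separate question. The randomised units are 20 facilities, and the planned tests are F tests in a model with a random facility effect. A power table built on normal critical values treats the between-facility variance as known.

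**Working it through.** **Inputs** (Section 11.2, I. Primary Outcome)
- 10 facilities per group, comparing the factorial margins with no interaction
- 60 patients per facility, so 600 per group
- ICC 0.10
- SD 0.08 or 0.10
- Significance level 0.05. Sidedness is not stated for the primary outcome; two-sided is stated for secondary outcomes in the same section, and it is what reproduces Table 5.

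**Formula.** Design effect = 1 + 59 × 0.10 = 6.9. SE = √(2 × SD² × 6.9 / 600) = SD × √0.023, which is 0.01213 at SD 0.08 and 0.01517 at SD 0.10. Power = Φ(D/SE − 1.960); the far tail is negligible.

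**Step 1: reproduce Table 5, then evaluate 3.0 points**

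| D | SD | D/SE | Power | Plan states |
|---|---|---|---|---|
| 0.034 | 0.08 | 2.802 | 80.0% | 80% |
| 0.034 | 0.10 | 2.242 | 61.1% | 61% |
| 0.040 | 0.08 | 3.297 | 90.9% | 91% |
| 0.043 | 0.10 | 2.835 | 80.9% | 81% |
| 0.030 | 0.08 | 2.473 | 69.6% | 80% (text) |

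The four cells match, so the method is identified by reproduction. The sentence on 3% does not match.

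**Step 2: what 80% at 3.0 points would take**
- D/SE must reach 1.960 + 0.842 = 2.802, so SE = 0.030 / 2.802 = 0.01071 and SD = 0.01071 / √0.023 = 0.0706. The plan's limit is 0.08.
- Facilities per group = 2.802² × 2 × 0.08² × 6.9 / (60 × D²). This is 9.99 at D = 0.034 and 12.84 at D = 0.030. Ten per group fits 0.034; 0.030 would need 13.

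**Step 3: variants that might rescue the sentence**
- 90 patients per facility: 71.5%.
- One-sided test: 79.6% at D = 0.030, but 87.7/72.5/95.1/88.3% for the Table 5 cells, so it is not the method used.

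**Step 4: the target.** 20% − 3.4 = 16.6%, and 20% − 4.3 = 15.7%. The range evaluated is therefore 15.7-16.6%. The 0.16-0.17 range is that range rounded; 15-16% is not.

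**Step 5: small-sample version (assumption).** Same SE, noncentral t. The df could be 18 (20 facilities, two groups), 17 (20 minus the intercept and two main effects) or 16.

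| D, SD | Normal | 18 df | 17 df | 16 df |
|---|---|---|---|---|
| 0.034, 0.08 | 80.0% | 75.5% | 75.2% | 74.9% |
| 0.034, 0.10 | 61.1% | 56.4% | 56.1% | 55.8% |
| 0.040, 0.08 | 90.9% | 87.6% | 87.4% | 87.2% |
| 0.043, 0.10 | 80.9% | 76.5% | 76.2% | 75.9% |
| 0.030, 0.08 | 69.6% | 64.8% | 64.5% | 64.2% |

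A simulation of 20 facility means with two main effects (200,000 runs, 17 df) agrees: 75.1%, 56.2%, 87.5%, 76.1% and 64.5% in the same order. The difference with 80% power moves from 3.4 to 3.6 points at SD 0.08, and from 4.2 to 4.5 points at SD 0.10.

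**The case against.** The best defence is that the plan discloses what it evaluated. The range 0.034 to 0.043 appears before the disputed sentences, Table 5 prints 0.034 above the 80%, and the first mention of 0.03 is marked as approximate. The stated target is also 15-16%, not 17%. That explains how the slip arose and shows that Table 5 is sound on its own method. It does not make the sentence right: the summary drops the approximation sign, and the gloss gives an exact pair of percentages that has 70% power.

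On degrees of freedom, the defence is stronger. The plan names no formula, so normal values are inferred from the match with Table 5, and the 16 to 18 df are not fixed by the documents. The patient-level covariates listed in Section 11.4 could recover power: with the ICC held at 0.10, an 11% cut in variance restores 80% at 3.4 points on 17 df. At 3.0 points the cut would have to be 22% with normal values or 31% on 17 df. Section 11.2 credits no such gain.

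A reader might infer more than the documents support:
- **That the 81% at SD 0.10 is also wrong.** The plan attaches 81% to 0.043, which is correct. The 20% versus 16% gloss is only loose rounding of 15.7%; an exact 4.0 points at SD 0.10 has 75% (0.040 / 0.01517 = 2.638), but the plan does not claim 81% for it.
- **That the secondary-outcome claims fail too.** The claims of "over 80% to detect differences of 6 or higher for ICC=0.2" on symptom burden and adequate power "to detect differences as small as 4.5 points for all three assumed sigma values" on quality of life hold on the plan's method (83%, and 82% at SD 12).
- **That the primary test will have an inflated type I error.** No section proposes a 1.96 cut-off for the analysis, and Section 4.1 plans F tests. The gap is an unnamed df method.

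**Conclusion.** The statement of 80% power for a 3-point difference is wrong by about 10 percentage points on the plan's own inputs: it should be about 70%. This needs no outside assumption beyond the two-sided normal method that reproduces Table 5. The 15-16% target is also out of line with the 15.7-16.6% evaluated; this is a minor inconsistency of wording.

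The small-sample point stands as a separate, conditional one. If the facility-level tests use about 16 to 18 df, the two Table 5 cells at 80% and 81% fall to about 75% and 76%, and the 3-point power to about 65%, before any covariate gain.

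The fault lies in the power statement and not in the design. At 4 points and SD 0.08, power is 91% as stated, and still about 87% with t critical values.

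**What to change.** In Section 11.2, I. Primary Outcome:
- Restate both sentences on the 3% difference as 80% power for 3.4 points (20% versus 16.6%) at SD 0.08, or as 70% for 3.0 points at SD 0.08.
- Write the gloss on 0.043 as 20% versus 15.7%; leave its 81% unchanged on the normal basis.
- Give one target, aligned with the 15.7-16.6% range evaluated.
- Restate Table 5 with t or F critical values under a stated df, and say whether any gain from covariate adjustment is assumed.

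In Section 11.4, name a small-sample denominator df method for the facility-level tests in MIXED; Kenward-Roger is one suitable choice.

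The cost is a text edit, one recomputed table and a less favourable stated power. No extra facilities or patients are needed.

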- e. By bed time
- f. By the next morning
- g. Before the next scheduled dialysis session
- h. Did not recover before the next scheduled dialysis session
- i. Patient unable or declined to answer

Furthermore, the Chairside system will require completion of this question once a week before the staff member begins the dialysis session. The patient care technicians and nurses will be trained prior to study start to record these data.

Responses to this variable will also be used as a secondary outcome for patient symptoms, alone and in combination with the patient symptom burden measure described above. This question will be asked once per week of every patient in the study.

Quality of life. Quality of life is a patient-reported outcomes, which is “any report of the status of a patient's health condition that comes directly from the patient, without interpretation of the patient's response by a clinician or anyone else.”¹²⁷ PRO instruments can be interviewer-administered, self-administered, computer-administered or interactively administered.¹²⁷ We will use the 36-item Kidney Disease Quality of Life (KDQOL™-36 Version 1),^{128, 129} which has good internal consistency based on alpha scores.¹²⁹ This instrument is required annually for US hemodialysis patients.¹³⁰ The quality of life survey, the Kidney Disease Quality of Life (KDQOL™-36 Version 1), is intended to be completed on at least an annual basis. KDQOL results will be provided twice for each patient from surveys available as follows: 1) The latest survey within 12 months prior to the start of the study intervention and 2) the earliest survey within 12 months after the start of the intervention. As is current procedure at FMCNA, the measure of quality of life is based on a self-administered survey by providing a paper copy to the patient to complete during treatment or at home. If a patient needs assistance, the Social Worker will assist patients during treatment or via phone in completion of the survey as needed or desired.

Hospitalization. These data will be gathered from FMCNA records for all patients. Hospitalizations within the study period will be calculated. Secondary analyses of this outcome will assess hospitalizations by cause using hospital discharge diagnosis (e.g., fluid-related or cardiovascular causes, COVID-19), number of hospitalizations per patient, and length of hospitalization.

Mortality. These data will be gathered from FMCNA patient records.

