7 STUDY SCHEDULE

The active intervention will begin in sets of four clinics at a time, each randomized to one of four treatments. See Schedule of Events in Appendix A for staggered roll out dates. The study coordinator will contact each clinic manager by phone -7 to -4 months from data collection start. The Study Coordinator helpline will be available during the preparation and enrollment periods, one month prior to data collection, in order to assist with patient or clinic questions. The study coordinator will schedule digital meetings for each provider education clinic in intervention weeks 1-3 to conduct the first online training and in weeks 4-6 to conduct the second online

training. Study coordinator(s) will be available by phone for questions or concerns throughout the study. See the Schedule of Events for an overview of the study schedule.

The patient activation intervention should take 5-6 weeks on average to complete. We anticipate staggered participation of patients in the patient activation intervention due to limits on the number of tablet computers and the number of peer mentors.

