Aim 2. Test and compare the effects of the two HD facility-level interventions on secondary patient-centered clinical outcomes, including: patient symptoms, fluid adherence, dialysis adherence, quality of life, hospitalizations and mortality over the same timeframe.

Aim 2 incorporates six outcome measures: (1) patient symptoms (including a patient burden measure, dialysis recovery time, and proportion of sessions with each symptom), (2), fluid adherence (inter-dialytic weight gain), (3) dialysis adherence, (4) quality of life, (5) hospitalization (all-cause and by specific cause), and (6) mortality (all-cause and by specific cause), with will be analyzed at the individual level and summarized at the facility level. Each

will use a model format appropriate to the outcome type, but will otherwise follow the model strategy, including the secondary analyses, described for Aim 2 above. This includes censoring of patient data while they are at another facility. The fluid adherence (Interdialytic weight gain), symptom and quality of life analyses, based on continuous outcome measures, will be carried out using mixed models (the MIXED procedure of SAS). Note that the quality of life analyses will be based on data from two time points, one before intervention and one during intervention, rather than session-specific data as analyzed for the other outcomes. Analyses of missed or shortened HD sessions will employ logistic regression for longitudinal data, as in Aim 2. Analyses of hospitalization and mortality will use logistic regression for individual level data. As part of these models, we will test IDH-related variables (e.g., recent IDH, frequency of IDH in the past month) as potential predictors. In each case, the appropriate regression diagnostics will be used to assess model fit.

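### The follow-up KDQOL has no minimum lag after intervention start, so it can be a survey completed before live training or mentoring, and the plan describes its timing inconsistently

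*Combined protocol and SAP*

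**What the plan says.** Section 3.2.2 defines the follow-up KDQOL as "the earliest survey within 12 months after the start of the intervention", and Section 11.2 II repeats the rule as "the earliest KDQOL survey that is within 12 months after the start of the intervention". Neither sets a minimum lag or ties the survey to training or mentoring dates. Section 3.2.2 adds that the instrument "is intended to be completed on at least an annual basis" and that results will be supplied twice per patient, so the rule also governs the data transfer.

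Exposure builds up after intervention start. Section 7 schedules the provider meetings "in intervention weeks 1-3 to conduct the first online training and in weeks 4-6 to conduct the second online" training. On mentoring it says "The patient activation intervention should take 5-6 weeks on average to complete" and "We anticipate staggered participation of patients in the patient activation intervention due to limits on the number of tablet computers". Section 5.4.1 lets patients who enter a facility up to week 18 join the list from which mentees are drawn.

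The timing of the follow-up survey is described in four ways:
- Section 3.2.4: quality of life is measured before and after the intervention.
- Section 11.2 II: the second survey falls during or after the intervention.
- Section 11.4, Aim 2: "one before intervention and one during intervention".
- Section 4.1 VIII: data collection at a facility ends with the post-intervention phase, which is 24 + 12 = 36 weeks after start. The survey window runs to 12 months.

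**The concern.** Quality of life rests on one follow-up survey per patient, so later, exposed weeks cannot offset a survey taken too early. A survey completed in week 1 reflects usual care in every arm, and including it shrinks the estimated difference. The covariate lists in Section 11.4 contain no survey-timing term, and no sensitivity analysis by survey date is planned.

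If only the earliest survey is transferred, an analyst who later wants a more exposed survey from the same patient will not have it. The conflicting descriptions also leave open whether surveys after week 24, or after week 36, count at all.

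**Working it through.** **Inputs (Section 11.2 II(d)).** ICC 0.07; 20 facilities of 60 patients, so 10 facilities per side for each main effect; SD 10 to 12; difference 4.5 points; stated power above 0.80. Alpha is 0.05, taken here as two-sided.

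**The plan's figure.**
- Effective n per side = 10 × 60 / (1 + 59 × 0.07) = 600 / 5.13 = 117.0.
- SE at SD 12 = 12 × √(2/117.0) = 1.569.
- Power = Φ(4.5/1.569 − 1.96) = Φ(0.908) = 0.82.
- At SD 11 and SD 10 the same formula gives 0.88 and 0.93.

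The stated figure reproduces under a normal approximation. A t reference on 18 degrees of freedom gives 0.77 at SD 12 before any dilution.

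**Share of early surveys.** The documents give no survey dates. Assume they are uniform over the window:
- before week 3: 3/52 = 5.8%
- before week 6: 6/52 = 11.5%
- before week 6 if surveys stop at week 36: 6/36 = 16.7%

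**Dilution against exclusion.** If a share f of surveys carries no effect, the expected difference is 4.5 × (1 − f) with 60 patients per facility. If those surveys are dropped, the difference stays at 4.5 with 60 × (1 − f) patients per facility.

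| Early share f | Diluted difference | Power, SD 10 | Power, SD 12 | Patients per facility if dropped | Power if dropped, SD 12 |
|---|---|---|---|---|---|
| 0 | 4.50 | 0.93 | 0.82 | 60 | 0.82 |
| 5.8% | 4.24 | 0.90 | 0.77 | 56.5 | 0.81 |
| 11.5% | 3.98 | 0.86 | 0.72 | 53.1 | 0.81 |
| 16.7% | 3.75 | 0.82 | 0.67 | 50 | 0.80 |

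Exclusion costs little. Going from 60 to 53.1 patients per facility moves the effective n only from 117.0 to 114.3, and the SE at SD 12 from 1.569 to 1.588 (about 1.2%).

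**Mentoring.** Start dates are not given either. If mentees start uniformly between week 2 and week 12, 18 or 22, the mean start is week 7, 10 or 12. The share of their surveys before the first session is then 7/52 = 13%, 10/52 = 19% or 12/52 = 23%. If the effect is scaled down by those shares, power at SD 12 is 0.70, 0.64 or 0.60.

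**The case against.** The strongest reply has five parts.

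- **How often it bites.** With roughly annual surveys, most patients have about one survey in the window, so the word earliest seldom chooses between two. A reader might infer that the rule systematically selects unexposed surveys. The documents do not support that: under uniform timing, 88-94% of surveys fall after week 6 or week 3. The missing lag is the cause, and replacing earliest with latest would not cure it. This part stands.
- **When exposure starts.** The first live session is in weeks 1-3, and Section 6.2.1 puts a computerised introduction before the live sessions. Zero effect through week 6 is therefore an upper-end assumption for the provider arm. This stands, and is why the 3-week figure is shown as well.
- **Which SD and difference.** Section 11.2 II(d) gives the KDQOL an SD of 10 and calls 5 points clinically meaningful. At 5 points and 11.5% dilution, power is 0.92 at SD 10 and 0.805 at SD 12. This limits the practical loss. With 16.7% dilution, 5 points at SD 12 gives 0.76.
- **Estimand.** Weight gain and recovery time are averaged over the whole 24 weeks, early weeks included, and Section 5.4.4 accepts attenuation from non-participation. But those outcomes average many sessions per patient, whereas the KDQOL is one snapshot, and Section 3.2.4 describes a before-and-after measure. This does not remove the problem.
- **Selection.** Later surveys come from patients who survive and stay, and Section 5.4.1 expects 15-20% turnover over 11 months. A 6-week shift adds little of this.

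**Conclusion.** The point holds in a limited form. The stated rule admits essentially unexposed surveys as follow-up, which biases the quality-of-life comparison towards no effect, and the sections disagree on when the survey falls.

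Under uniform survey dates, about 6-17% of surveys are affected. Power for 4.5 points falls from 0.82 to between 0.77 and 0.67 at SD 12, and from 0.93 to between 0.90 and 0.82 at SD 10. These figures rest on assumed survey dates, no effect at all before the cut-off, and 4.5 points as the effect in exposed patients. They are a range, and the actual loss is not known. Surveys clustered soon after start would make it larger; partial early exposure would make it smaller.

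A reader might also infer that the trial's main result is at risk. It is not: the primary outcome comes from session records, and Section 11.2 II says the study was not powered specifically for the secondary outcomes. This is a cheap improvement to a secondary outcome.

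**What to change.** - Define the follow-up KDQOL as the earliest survey at or after week 6, when the second live training is due to be complete, within one stated window. Apply it identically in all arms. The four facilities of an implementation group start together, so week 6 is defined for control facilities too.
- Request every KDQOL survey in the window, with its date, so that later ones are available.
- Keep the current rule as a sensitivity analysis. Add a later cut-off, for example week 12, for the mentoring comparison, because week 6 does not fully remove the dilution there. Under uniform timing, dropping surveys before week 12 (12/52 = 23%) still leaves power of 0.80 at SD 12.
- Weeks since start may be added as a covariate, but a main effect of time does not itself remove the dilution.
- Align Sections 3.2.2, 3.2.4, 4.1 VIII, 11.2 II and 11.4 on the window, and state whether surveys after week 36 are collected.

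The cost is SAP wording and a revised data request. The downside is fewer follow-up surveys: about 6% with a week-3 cut, and 12-17% with week 6, less any patients who have a later survey in the window. There is also slightly more selection of patients who remain.
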